7.5.4 Day 14 (week two) +/- 1 day

- a. vital signs
- b. slit lamp and fundus exam
- c. BCVA
- d. IOP
- e. con meds
- f. adverse events
- g. blood sample for Ab testing

7.5.5 Day 21 (week three) +/- 1 day

- a. vital signs
- b. slit lamp and fundus exam
- c. BCVA
- d. IOP
- e. con meds
- f. adverse events

7.5.6 Day 28 (week four/month 1) +/- 1 day

- a. brief medical history and physical exam, including any changes in vision or light perception reported by patient or noted by study staff since prior H& PE
- b. vital signs
- c. CBC, platelet, differential, hemoglobin, hematocrit
- d. blood chemistries, not limited to, but must include AP, ALT, AST, BUN, Cr, total bilirubin, serum electrolytes, glucose, calcium, phosphate, albumin and total protein
- e. coagulation function, including PT/INR, PTT only participants who had abnormal values (out of normal range) at baseline
- f. slit lamp and fundus exam
- g. BCVA
- h. IOP
- i. OCT
- j. con meds
- k. adverse events
- 1. blood sample for Ab testing

7.5.7 Month 2 (Day 60) +/- 4 days

- a. vital signs
- b. slit lamp and fundus exam
- c. BCVA

- d. IOP
- e. exploratory visual assessments
- f. con meds
- g. adverse events

7.5.8 Month 3 (Day 90) +/- 4 days

- a. brief medical history and physical exam, including any changes in vision or light perception reported by patient or noted by study staff since prior H & PE
- b. vital signs
- c. CBC, platelet, differential, hemoglobin, hematocrit
- d. blood chemistries, not limited to, but must include AP, ALT, AST, BUN, Cr, total bilirubin, serum electrolytes, glucose, calcium, phosphate, albumin and total protein
- e. coagulation function, including PT/INR, PTT only participants who had abnormal values (out of normal range) at baseline
- f. urinalysis
- g. slit lamp and fundus exam
- h. BCVA
- i. B-scan
- j. IOP
- k. OCT
- 1. exploratory visual assessments
- m. con meds
- n. adverse events

7.5.9 Month 4 (Day 120) +/- 4 days

- a. vital signs
- b. slit lamp and fundus exam
- c. BCVA
- d. IOP
- e. con meds
- f. adverse events

7.5.10 Month 5 (Day 150) +/- 4 days

- a. vital signs
- b. BCVA
- c. IOP
- d. con meds
- e. adverse events

7.5.11 Month 6 (Day 180) +/- 4 days

- a. brief medical history and physical exam, including any changes in vision or light perception reported by patient or noted by study staff since prior H & PE
- b. vital signs
- c. CBC, platelet, differential, hemoglobin, hematocrit
- d. blood chemistries, not limited to, but must include AP, ALT, AST, BUN, Cr, total bilirubin, serum electrolytes, glucose, calcium, phosphate, albumin and total protein
- e. coagulation function, including PT/INR, PTT only participants who had abnormal values (out of normal range) at baseline
- f. urinalysis
- g. slit lamp and fundus exam
- h. BCVA
- i. B-scan
- j. IOP
- k. ERG
- 1. OCT
- m. FA only if cystoid macular edema (CME) is observed on OCT
- n. AF
- o. VF (if applicable)
- p. con meds
- q. adverse events
- r. exploratory visual assessments

7.5.12 Month 9 (Day 270) +/- 4 days

- a. vital signs
- b. slit lamp and fundus exam
- c. BCVA
- d. IOP
- e. exploratory visual assessments
- f. con meds
- g. adverse events

7.6 End of Treatment (Month 12) or Early Termination Visit

- a. MH and physical exam, including weight and height
- b. vital signs
- c. pregnancy test (if applicable)
- d. CBC, platelet, differential, hemoglobin, hematocrit

- e. blood chemistries, not limited to, but must include AP, ALT, AST, BUN, Cr, total bilirubin, serum electrolytes, glucose, calcium, phosphate, albumin and total protein
- f. coagulation panel, including PT/INR, PTT
- g. urinalysis
- h. slit lamp and fundus exam
- i. BCVA
- j. B-scan
- k. ERG
- 1. IOP
- m. OCT
- n. FA
- o. VF (if applicable)
- p. con meds
- q. adverse events
- r. blood sample for Ab testing
- s. exploratory visual assessments
- t. informed consent for follow-up study

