6.0 TREATMENT PLAN

6.1 Dose and Schedule

All subjects will receive a single intravitreal injection of hRPC at the assigned dose into the eye with the poorest visual acuity or, if vision is comparable in both eyes, the non-dominant eye. After topical anesthesia, a single 50 microliter suspension of cells (0.5, 1, 2 or 3 million) will be delivered under direct visualization into the vitreous cavity using a 30 g needle. This treatment does not require surgical detachment or manipulation of the retina. The injection procedure itself takes approximately 2 minutes. Following 60 minutes of observation with no serious clinical symptoms or manifestations (IOP < 30 mm Hg and vital signs comparable to pre-treatment), subjects will be released to home on the day of injection. Please refer to the study procedure manual for details of patient preparation and monitoring.

The schedule of observations and assessments during the study are summarized in Table 2.

jCyte, Inc Protocol No. JC-01

				I able A	2 Sche	aule of .	Assessm	ents (JC	Ĵ - 01)							
Timepoint	Scr	BL*	Day 0	Day 1	Day 2	Day 7 ⁷	Day 14 ⁷	Day 21 ⁷	Day 28 ⁷	M 2 ⁸	M3 ⁸	M4 ⁸	M5 ⁸	M6 ⁸	M9 ⁸	M12 or Early Term
Written informed consent	Х															
Medical history (MH)	Х	x*														Х
Physical examination (PE)	Х	x*														х
Brief MH and PE				х		Х			X		X			Х		
HLA typing	Х															
Weight	Х	x*	Х			Х										Х
Vital signs	Х	х	Х	Х	Х	х	Х	х	Х	Х	Х	Х	Х	Х	х	Х
Pregnancy test	Х	x*														х
Safety laboratory tests ¹	Х	x*				х			Х		Х			Х		Х
Infectious disease tests ²	Х	x*														
Urinalysis ³	Х	x*									Х			Х		х
Electrocardiogram	Х	x*	х	Х												
Slit lamp and fundus exam	Х	x ⁴		х	х	Х	Х	х	X	х	X	X	Х	Х	х	Х
BCVA (ETDRS)	Х	x	х	х	х	Х	Х	х	X	х	X	X	Х	Х	х	Х
ERG	x ⁹	x ⁹												Х		Х
IOP		x	х	х	х	Х	Х	х	X	х	X	X	Х	Х	х	Х
OCT		х							Х		Х			Х	х	Х
FA		х												x ⁶		х
AF		х												Х		х
VF (if applicable)		x												Х		Х
B-scan		х				Х					X			Х		Х
Exploratory non-invasive visual assessments (optional)		х									х			х	х	х
Study Drug Injection			х													
Con Meds			Х	х	х	х	х	х	х	х	х	х	Х	Х	Х	Х
Adverse events			х	х	х	х	х	х	х	х	х	х	Х	Х	Х	Х
Blood sample for Ab testing ⁵		х					Х		х							Х
Written consent for FU study																Х
		·				*	*	·					•			

 Table 2 Schedule of Assessments (JC -01)

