7.5.3 Day 7 (week one)

- a. brief medical history and physical exam, including any changes in vision or light perception reported by patient or noted by study staff since prior H & PE
- b. weight
- c. vital signs
- d. CBC, platelet, differential, hemoglobin, hematocrit
- e. blood chemistries, not limited to, but must include AP, ALT, AST, BUN, Cr, total bilirubin, serum electrolytes, glucose, calcium, phosphate, albumin and total protein
- f. coagulation function, including PT/INR, PTT only participants who had abnormal values (out of normal range) at baseline
- g. slit lamp and fundus exam
- h. BCVA
- i. B-scan
- j. IOP
- k. con meds

l. adverse events

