8.1.5 Ophthalmic AEs

Procedures will be performed at scheduled intervals to specifically assess eye AEs that may not be detected by usual AE reporting. Please refer to the study procedure manual for details of all ophthalmologic assessment procedures.

Slit lamp and fundus exam - The binocular slit-lamp examination provides a stereoscopic magnified view of the eye structures in detail, enabling anatomical diagnoses to be made for a variety of eye conditions. This assessment will include detection of anterior chamber cell or flare; acute cataract development or progression in phakic patients, or vitreous haze. Fundus exam allows for inspection of the retina, the cellular graft, and detection of retinal detachment.

B-scan – B-scan is a test that uses high-frequency sound waves to get measurements and produce detailed images of the eye. This test may provide information regarding the location of the injected cells and the size of the cell clusters at different time points during the study.

IOP - Intraocular pressure is measured with a tonometer as part of a comprehensive eye examination. Measured values of intraocular pressure are influenced by corneal thickness and rigidity

Spectral Domain Optical Coherence Tomography (OCT) - A clinical OCT machine will be used for data collection; the same machine should be used for any given patient at each time point. OCT tests, including assessment of the ellipsoid zone (EZ), will be analyzed to help define retinal anatomy, and will enable monitoring for ocular inflammation after treatment as manifest by cystoid macular edema or epiretinal membrane formation or progression.

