8.1 Efficacy Variables

The response to jCell injection will be assessed based on the following:

- Best Corrected Visual Acuity (BCVA): BCVA will be measured with the electronic visual acuity testing algorithm (E-ETDRS). For each time point assessed, the total number of letter missed using E-ETDRS will be recorded for each eye and recorded on the Best Corrected Visual Acuity (BCVA) case report form.
- Electroretinogram (ERG): For each eye, A-wave Amplitude, B-wave Amplitude, Time from Flash Onset to A-wave Trough and Time from Flash Onset B-wave peak will be measured under the following conditions:
 - Dark adapted 0.01 ERG (rod response)
 - Dark adapted 3.0 ERG (rod-cone response)
 - Light adapted 3.0 ERG (single flash cone response)
 - Light adapted 3.0 flicker ERG

In addition, an overall assessment of Normal or Abnormal will be recorded for each condition. For those assessments of Abnormal, whether the assessment was Clinically Significant will also be reported. If Clinically Significant value is not reported in the follow-up visit, then the value will be imputed based on the value of previous visit, consistent with CRF completion guidelines. For example, if abnormal change from previous visit is "NO" then imputed value will be value from the previous visit.

• Optical Coherence Tomography (OCT): for assessment of OCT, the central subfield thickness reported on the Optical Coherence Tomography case report

jCyte, Inc	Statistical Analysis Plan
Protocol No. JC-01	08Nov2017

form will be used. Also information recorded at each visit as to whether Cystoid macular edema (CME) was present and if so, did it involve the foveal center will also be considered.

- Fluorescein Angiography: information regarding active leakage (Yes/No) and ischemia (Yes/No) will be collected for each eye for each Fluorescein Angiography performed.
- Autofluorescence: an overall assessment of Normal or Abnormal will be recorded for each eye for each fundus auto fluorescence imaging performed. For those assessments of Abnormal, whether the assessment was Clinically Significant will also be reported. If Clinically Significant value is not reported in the follow-up visit, then the value will be imputed based on the value of previous visit, consistent with CRF completion guidelines. For example, if abnormal change from previous visit is "NO" then imputed value will be value from the previous visit.

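### Protocol visit lists 7.5.10, 7.5.12 and 7.6 omit three examinations that Table 2 schedules: slit lamp/fundus at Month 5, OCT at Month 9 and autofluorescence at Month 12/Early Termination

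*Protocol*

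**What the plan says.** Protocol section 6.1 states: "The schedule of observations and assessments during the study are summarized in Table 2". In that table the slit lamp and fundus row is marked at Month 5, the OCT row at Month 9, and the AF row in the Month 12/Early Termination column.

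Section 7 then gives a lettered list for each visit:

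- "7.5.10 Month 5 (Day 150) +/- 4 days" lists vital signs, BCVA, IOP, concomitant medications and adverse events. There is no slit lamp or fundus examination.
- "7.5.12 Month 9 (Day 270) +/- 4 days" lists vital signs, slit lamp and fundus, BCVA, IOP, exploratory assessments, concomitant medications and adverse events. There is no OCT.
- "7.6 End of Treatment (Month 12) or Early Termination Visit" includes OCT, fluorescein angiography and visual field, but not AF.

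SAP section 3 points to Table 2 of the protocol for the schedule and does not mention the Section 7 lists. SAP Appendix C has Month 5 rows for slit lamp and dilated fundoscopy, a Month 9 row for OCT and a Month 12/Early Termination row for AF. SAP section 8.1 counts AF among the efficacy variables: "Autofluorescence: an overall assessment of Normal or Abnormal will be recorded for each eye for each fundus auto fluorescence imaging performed".

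**The concern.** Safety is the primary objective. Protocol section 3.2.2 names slit lamp findings and the absence of clinically significant epiretinal membrane among the safety criteria. Section 8.1.5 says that OCT "will enable monitoring for ocular inflammation after treatment as manifest by cystoid macular edema or epiretinal membrane formation or progression". The examinations in question therefore serve a stated purpose.

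A site that builds its worksheets from Section 7 would skip one ocular safety examination, leave the second half of follow-up with no OCT until Month 12, and obtain no final AF. Section 7.6 also governs early termination, so a subject who leaves before Month 6 would have no AF after injection at all.

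There is a second cost. Section 11.4 asks monitors to verify adherence to the schedule, and SAP section 7.2 lists every protocol deviation. With two conflicting schedules, nobody can say whether a missing Month 9 OCT is a deviation.

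**Working it through.** No sample size or power figure is involved. The check is a comparison of marked visits followed by counting.

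**Follow-up visits (after Day 0)**

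| Test | Marked in Table 2 | Count | Absent from Section 7 | Count in Section 7 |
|---|---|---|---|---|
| Slit lamp/fundus | D1, D2, D7, D14, D21, D28, M2, M3, M4, M5, M6, M9, M12 | 13 | M5 | 12 |
| OCT | D28, M3, M6, M9, M12 | 5 | M9 | 4 |
| AF | M6, M12 | 2 | M12 | 1 |
| Total | | 20 | 3 | 17 |

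Each of the three Table 2 rows fills exactly 16 visit columns, and the three lists are lettered without gaps, so this is not an artefact of text extraction. Section 7.5.11 does name OCT and AF at Month 6, so Section 7 lists these tests by name elsewhere.

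**Loss per subject if Section 7 alone is followed**

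- Slit lamp/fundus: 1/13 = 7.7%
- OCT: 1/5 = 20%
- AF: 1/2 = 50%. For a subject who terminates before Month 6 the count goes from 1 to 0.

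**Intervals between examinations**

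- OCT after Month 6, Table 2: 270 − 180 = 90 days. With ±4 days at each end this is 82 to 98.
- OCT after Month 6, Section 7: section 7.6 gives no day for Month 12. Taking Day 360 to 365 as an assumption, 360 − 180 = 180 and 365 − 180 = 185 days.
- Slit lamp/fundus after Month 4, Table 2: 150 − 120 = 30 days (22 to 38).
- Slit lamp/fundus after Month 4, Section 7: 180 − 120 = 60 days (52 to 68).

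**SAP tables with an affected visit row**

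- Slit lamp: 14.3.4.6.1 and .2
- Dilated fundoscopy: 14.3.4.10.1 and .2
- OCT: 14.3.4.12.1 and .2
- AF: 14.3.4.14.1 and .2

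That is 2 + 2 + 2 + 2 = 8 tables, or four assessments each shown for two eyes.

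**The case against.** The best defence is that this is clerical. Table 2 already schedules all three tests, the protocol directs readers to it, and the SAP relies on it alone for the schedule. Sites also had case report forms and a study procedure manual, which we cannot see. The subject-level listings carry Month 5 slit lamp and fundoscopy and Month 12 AF. No escalation rule or stopping rule changes. Timing also matters: the protocol gives a 2015–2016 study period and its last amendment is dated July 2016, while the SAP is dated November 2017. A protocol edit may therefore come after the last visit.

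Much of this stands. It supports reading Table 2 as the intended schedule, and it makes the harm conditional. It does not remove the contradiction: the lists are operative instructions, and no sentence ranks them below the table. The SAP layouts are also imperfect evidence of intent. They contain Day 3 rows that Table 2 does not schedule, and a note under fluorescein angiography extends that table to an unscheduled Month 9.

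The SAP also already covers most of the data handling. Section 8.3 uses observed data only. The slit lamp, fundoscopy and AF layouts print a per-visit n and base percentages on results reported, and the OCT layout prints n/N.

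**Conclusion.** The inconsistency is real at three points and should be corrected. If Section 7 alone was followed, the loss is one examination of each type per subject, three of 20 scheduled. The largest effects are on AF and on the OCT interval after Month 6. The interval figure depends on Month 12 falling at Day 360 to 365. Every loss figure depends on which text sites used, which the documents do not show.

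A reader might infer more than this, but the documents do not support it:

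- **That data were lost.** Nothing shows that any site skipped an examination.
- **That the 12-month outcome is compromised.** BCVA, ERG, OCT and visual field are all in list 7.6. Month 9 keeps slit lamp/fundus, BCVA, IOP and adverse events; Month 5 keeps BCVA, IOP and adverse events.
- **That an ellipsoid zone analysis suffers.** The SAP plans none. Section 10.7.6 tabulates only cystoid macular edema and foveal involvement.
- **That Table 14.3.4.11 is a ninth affected table.** It reports a separate post-injection vitreous examination. It starts on Day 0, when Table 2 schedules no slit lamp or fundus examination, and SAP section 10.7.5 accepts indirect ophthalmoscopy and other methods.
- **That the missing Month 9 in OCT Listing 16.2.6.3 is part of the same error.** Other listing layouts drop scheduled visits too: BCVA omits Month 5, and vital signs omits Month 6. These are layout gaps.

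**What to change.** Add the slit lamp and fundus examination to 7.5.10, OCT to 7.5.12 and AF to 7.6. This is an administrative amendment of three list lines and asks for nothing beyond Table 2. The SAP table rows for these assessments need no change.

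I would not replace these lines with a general sentence that Table 2 governs. Under "7.5.7 Month 2 (Day 60) +/- 4 days" the protocol lists exploratory assessments that Table 2 does not mark, and they would drop out. Section 7 also limits follow-up coagulation tests before Month 12 to "only participants who had abnormal values (out of normal range) at baseline", whereas the Table 2 footnote includes the coagulation panel in the safety laboratory tests without that limit.

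If follow-up is already complete, record in the study report which schedule sites used, and treat examinations not done as missing, as SAP section 8.3 provides. The SAP rule that carries forward an unreported clinical significance rating should not be read as filling in an examination that never took place.

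Two further changes are optional tidying. Adding Month 9 to Listing 16.2.6.3 is permitted by SAP Appendix A during programming. Showing number tested out of number still in follow-up would make gaps easier to see.

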8.0 ASSESSMENTS

8.1 Safety Assessments

8.1.1 Adverse Events

Subjects will be monitored for AEs from the time the subject receives a study number until the study end or early termination. Adverse events that occur between clinic visits will be elicited by direct, non-leading questioning or will be recorded if offered voluntarily by the subject. Further details for AE reporting can be found in Section 9.

8.1.2 Vital Signs

Blood pressure and heart rate, body temperature and respiratory rate will be recorded at screening, before and after intravitreal injection and at all follow-up visits.

8.1.3 Clinical Laboratory Tests

Blood samples for clinical laboratory tests will be taken as indicated in Table 2.

Hematology – full blood count including red blood cell (RBC) count, hemoglobin, hematocrit, white blood cell (WBC) count with differential and platelet count; neutrophils, lymphocytes, monocytes, eosinophils, basophils.

Biochemistry – alanine aminotransferase (ALT), aspartate aminotransferase (AST), alkalinephosphatase (AP), blood urea nitrogen (BUN), creatinine, total bilirubin, serum electrolytes,glucose, calcium, phosphate, albumin and total proteinCONFIDENTIAL29 of 41

Coagulation – PT/INR, PTT

Urinalysis – pH, protein, ketones, glucose, bilirubin, blood, urobilinogen, specific gravity by dipstick and microscopy if any findings are abnormal.

Pregnancy A urine sample will be collected for a pregnancy test at screening for female subjects of childbearing potential to test for pregnancy. If this is found to be positive, it will be followed up with a serum pregnancy test.

8.1.4 Blood Samples for Antibody Testing

Blood samples will be collected for testing for Panel Reactive Antibodies (PRA) and Donor Reactive Antibodies (DRA) prior to treatment, at 2 and 4 weeks post-treatment, and at study termination. Details of preparation/shipping of samples will be provided separately.

8.1.5 Ophthalmic AEs

Procedures will be performed at scheduled intervals to specifically assess eye AEs that may not be detected by usual AE reporting. Please refer to the study procedure manual for details of all ophthalmologic assessment procedures.

Slit lamp and fundus exam - The binocular slit-lamp examination provides a stereoscopic magnified view of the eye structures in detail, enabling anatomical diagnoses to be made for a variety of eye conditions. This assessment will include detection of anterior chamber cell or flare; acute cataract development or progression in phakic patients, or vitreous haze. Fundus exam allows for inspection of the retina, the cellular graft, and detection of retinal detachment.

B-scan – B-scan is a test that uses high-frequency sound waves to get measurements and produce detailed images of the eye. This test may provide information regarding the location of the injected cells and the size of the cell clusters at different time points during the study.

IOP - Intraocular pressure is measured with a tonometer as part of a comprehensive eye examination. Measured values of intraocular pressure are influenced by corneal thickness and rigidity

Spectral Domain Optical Coherence Tomography (OCT) - A clinical OCT machine will be used for data collection; the same machine should be used for any given patient at each time point. OCT tests, including assessment of the ellipsoid zone (EZ), will be analyzed to help define retinal anatomy, and will enable monitoring for ocular inflammation after treatment as manifest by cystoid macular edema or epiretinal membrane formation or progression.

8.2 Efficacy Assessments

Please refer to the study procedure manual for details of all ophthalmologic assessment procedures.

8.2.1 BCVA

BCVA will be tested at scheduled time points in both the treated and the contralateral eye. Visual acuity will be measured with the electronic visual acuity testing algorithm (E-ETDRS). E-ETDRS testing will be conducted using the electronic visual acuity tester (EVA). Based on estimates of 95% confidence intervals, a change in visual acuity of 0.2 logMAR (10 letters) from a baseline level is unlikely to be related to measurement variability using either the E-ETDRS or the S-ETDRS visual acuity testing protocol.

8.2.2 Electroretinogram (ERG)

ERG examinations will be performed according to ISCEV standards and standardized among clinics to minimize difference between centers: briefly, patients are dark adapted for 30 min, electrodes attached under dim red illumination (dark room safe light). ERG responses will be recorded using single scotopically-balanced dim blue and red light flashes, and bright white flashes per detailed protocol. ERG at 6, 12 months are compared to pre-injection in terms of 1) a-wave amplitude, 2) b-wave amplitude, 3) time from flash onset to a wave trough and 4) time from flash onset to b-wave peak. In individual patients significantly faster deterioration of injected eye by ERG parameters and BCVA will halt further enrollment, although the latter measure is likely to be the more informative.

